4.6.3.3.2. Liver Enzymes

Common analyses for laboratory analyte measurements described in Section 4.6.5 are applicable for the liver enzyme related measurements. This section describes additional analyses for liver enzymes.

For the postbaseline maximum value, all planned and unplanned measurements will be included. When or if multiple values are available (that is, unplanned measurement) prior to randomization, the maximum value will be used as baseline. Table GPIF.4.6 describes the planned analyses related to hepatic safety.

Table GPIF.4.6. Summary Tables and Figures Related to Hepatic Safety

| Analysis | Population or Analysis Set |
|---|----------------------------|
| Abnormal Postbaseline Categories – Hepatic Safety Parameters 
 • ALT: The number and percentage of participants with a measurement greater than or equal to 1 time (1\times), 3 times (3\times), 5 times (5\times), 10 times (10\times), and 20 times (20\times) the performing laboratory ULN during the treatment period for all participants with a postbaseline value and for subsets based on the following levels of baseline value: 
 ○ participants whose nonmissing maximum baseline value is $\leq 1 \times$ ULN, ○ participants whose maximum baseline is $>1 \times$ ULN, ○ participants whose baseline values are missing. • AST: The number and percentage of participants with a measurement greater than or equal to 1 time (1\times), 3 times (3\times), 5 times (5\times), 10 times (10\times), and 20 times (20\times) the performing laboratory ULN during the treatment period for all participants with a postbaseline value and for subsets based on various baseline levels, as described above for ALT. • ALP: The number and percentage of participants with a measurement greater than or equal to 2 times (2\times), and 3 times (3\times) the performing laboratory ULN during the treatment period will be summarized for all participants with a postbaseline and for the following subsets based on the baseline values: 
 ○ participants whose nonmissing maximum baseline value is $\leq 1 \times$ ULN, ○ participants whose maximum baseline is $>1 \times$ ULN, but $<2 \times$ ULN, ○ participants whose maximum baseline value is $\geq 2 \times$ ULN, and ○ participants whose baseline values are missing. • TBL: The number and percentage of participants with a measurement greater than or equal to 2 times (2\times), 5 times (5\times), and 8 times (8\times) the performing laboratory ULN during the treatment period will be summarized for all participants with a postbaseline value and the same subsets as described for ALP. • DBL: The number and percentage of participants with a measurement greater than or equal to 2 times (2\times) and 5 times (5\times) the performing laboratory ULN during the treatment period will be summarized for all participants with a postbaseline value and the same subsets as described for ALP. • GGT: The number and percentage of participants with a measurement greater than or equal to 2 times (2\times) the performing laboratory ULN during the treatment period will be summarized for all participants with a postbaseline value. | Safety Participants |
| Hepatocellular Drug-Induced Liver Injury Screening Plot (TBL vs. ALT or AST). | Safety Participants |
| Hepatocellular Drug-Induced Liver Injury Screening Table. | Safety Participants |

| Analysis | Population or Analysis Set |
|--|----------------------------|
| Cholestatic Drug-Induced Liver Injury Screening Plot (TBL vs. ALP). | Safety Participants |
| Cholestatic Drug-Induced Liver Injury Screening Table. | Safety Participants |
| 
Participant profiles will be created for participants meeting criteria for a comprehensive hepatic evaluation (as defined in the protocol).
 
Participant profiles will include demographics, disposition, information collected on the hepatic safety CRFs (where applicable) and a display of study drug exposure, adverse events, medications, blood pressure, heart rate, and the liver -related measurements over time.
 | Safety Participants |

Abbreviations: ALP = alkaline phosphatase; ALT = alanine aminotransferase; AST = aspartate aminotransferase; CRF = case report form; DBL = direct bilirubin; GGT = gamma-glutamyl transferase; TBL = total bilirubin; ULN = upper limit of normal.

4.6.3.4. Hypoglycemia

The following categories in accordance with the 2020 American Diabetes Association position statement on glycemic targets (ADA 2020) will be defined in the database.

Level 1 hypoglycemia

Glucose <70 mg/dL (3.9 mmol/L) and ≥54 mg/dL (3.0 mmol/L): Level 1 hypoglycemia can alert a person to take action such as treatment with fast-acting carbohydrates. Providers should continue to counsel participants to treat hypoglycemia at this glucose alert value.

Level 2 hypoglycemia

Glucose <54 mg/dL (3.0 mmol/L): Level 2 hypoglycemia is also referred to as documented or BG confirmed hypoglycemia with glucose <54 mg/dL (3.0 mmol/L). This glucose threshold is clinically relevant regardless of the presence or absence of symptoms of hypoglycemia.

Level 3 hypoglycemia

Severe hypoglycemia (in adults): A severe event characterized by altered mental and/or physical status requiring assistance for treatment of hypoglycemia. For example, participants had altered mental status, and could not assist in their own care, or were semiconscious or unconscious, or experienced coma with or without seizures, and the assistance of another person was needed to actively administer carbohydrate, glucagon, or other resuscitative actions. Glucose measurements may not be available during such an event, but neurological recovery attributable to the restoration of glucose concentration to normal is considered sufficient evidence that the event was induced by a low glucose concentration.

- The determination of a hypoglycemic event as an episode of severe hypoglycemia, as defined above, is made by the investigator based on the medical need of the participant to have required assistance and is not predicated on the report of a participant simply having received assistance.

- If a hypoglycemic event meets the criteria of severe hypoglycemia, the investigator must record the event as serious on the AE CRF and report it to Lilly as an SAE.

Nocturnal hypoglycemia

Nocturnal hypoglycemia is a hypoglycemia event (including severe hypoglycemia) that **occurs at night** and presumably during sleep.

To avoid duplicate reporting, all consecutive BG values <70 mg/dL (<3.9 mmol/L) occurring within a 1-hour period may be considered to be a single hypoglycemic event (Weinberg et al. 2010; Danne et al. 2013).

[figure not shown]
Summary and analyses of Level 2 or Level 3 hypoglycemic events will be performed.

4.6.3.5. Immunogenicity

4.6.3.5.1. *Definitions of Sample ADA Status*

At a high level, an individual sample is potentially examined multiple times, in a hierarchical procedure, to produce a sample ADA assay result and potentially multiple cross-reactive antibodies assay results and multiple Nab assay results.

The cut points used, the drug tolerance of each assay, and the possible values of titers are operating characteristics of the assay. [Figure GPIF.4.1](#) details a flow chart that reflects the multitiered testing approach.

Abbreviations: ADA = anti-drug antibody; CP = cut point; GIP = glucose-dependent insulinotropic polypeptide; GIPR = glucose-dependent insulinotropic polypeptide receptor; GLP-1 = glucagon-like peptide-1; GLP-1R = glucagon-like peptide-1 receptor; nGIP = native GIP; nGLP-1 = native GLP-1; LY = LY3298176; Nab = neutralizing antibodies.

Figure GPIF.4.1. Flowchart of immunogenicity multitiered testing approach.

Table GPIF.4.7 outlines results as reported from Tier 2a of the multitiered testing approach. Tier 4 results are reported similarly.

Table GPIF.4.7. Sample ADA Assay Results

| Sample Laboratory Result | Explanation |
|--------------------------|---|
| Detected | ADA are detected and confirmed. |
| Not Detected | The raw result as reported from the laboratory indicates not detected. The clinical interpretation of such results depends on other factors (see Table GPIF.4.8). |
| NO TEST, QNS, and so on. | Sample exists but was unevaluable by the assay. |

Abbreviations: ADA = anti-drug antibody; QNS = quantity not sufficient.

It can be the case that the presence of high concentrations of tirzepatide will affect ADA immunoassays, and conversely high levels of ADA may affect the measurement of tirzepatide concentration. Thus, a tirzepatide drug concentration, assessed from a sample drawn at the same time as the ADA sample, plays a key role in clinical interpretation of a sample when the laboratory result is Not Detected (see [Table GPIF.4.8](#)).

Table GPIF.4.8. Sample Clinical ADA Interpretation Results

| Sample Clinical Interpretation | Explanation |
|--------------------------------|--|
| ADA Present | ADA assay result is Detected |
| ADA Not Present | ADA assay result is Not Detected and simultaneous drug concentration is at a level that has been demonstrated to not interfere in the ADA detection method (i.e., drug concentration is below the assay's drug tolerance level). For participants receiving placebo, drug concentration is not assessed and is assumed to be below the assay's drug tolerance level. If drug concentration was planned but is not available for a treatment period sample, a Not Detected sample will be declared ADA Not Present. |
| ADA Inconclusive | ADA assay result is Not Detected but drug concentration in the sample is at a level that can cause interference in the ADA detection method. |
| ADA Missing | ADA sample not drawn, QNS, not tested, and so on, causing there to be no laboratory result reported or the result is reported as "no test." |

Abbreviations: ADA = antidiug antibody; QNS = quantity not sufficient.

All ADA Present samples will be evaluated for cross-reactive GIP (Tier 2b), cross-reactive GLP-1 (Tier 2c), Nab LY (tirzepatide) on GIPR (Tier 4a), and Nab LY (tirzepatide) on GLP-1R (Tier 4b).

Similar terminology to [Table GPIF.4.8](#) applies for each type of cross-reactive and Nab assay. Importantly, each of these are distinct assays and, in general, have different assay operating characteristics. The following are considered inconclusive for the Nab result:

- Nab LY on GIPR: if Nab result is not detected, and PK concentration is greater than or equal to drug tolerance limit of the Nab LY on GIPR assay
- Nab LY on GLP-1R: if Nab result is not detected, and PK concentration is greater than or equal to drug tolerance limit of the Nab LY on GLP-1R assay

For cross-reactive Nab interpretations against native GIP and GLP-1, an *in silico* method utilizing results from Tiers 2b and 2c, Tiers 4a and 4b, and tirzepatide concentrations is introduced. The *in silico* method is outlined in [Table GPIF.4.9](#).

Table GPIF.4.9. In Silico Classification for Cross-Reactive Nab

| In Silico Classification | Cross-Reactive ADA Result | Nab Result | Circulating Tirzepatide Level (ng/mL) | In Silico Cross- Reactive Nab Interpretation |
|------------------------------------|------------------------------|--|---|---|
| Cross-reactive Nab to nGIP | Tier 2b: "Not Detected" | Tier 4a: "Not Detected" Or Tier 4a: "Detected" or N/A or Missing | Any Value or Missing | Not Present |
| | Tier 2b: "Detected" | Tier 4a: "Not Detected" | < drug tolerance limit of Tier 4a assay | Not Present |
| | Tier 2b: "Detected" | Tier 4a: "Not Detected" | ≥ drug tolerance limit of Tier 4a assay | Inconclusive |
| | Tier 2b: "Detected" | Tier 4a: "Detected" | < drug tolerance limit of Tier 4a assay | Present |
| | Tier 2b: "Detected" | Tier 4a: "Detected" | ≥ drug tolerance limit of Tier 4a assay | Present |
| Cross-reactive Nab to nGLP-1 | Tier 2c: "Not Detected" | Tier 4b: "Not Detected" Or Tier 4b: "Detected" or N/A or Missing | Any Value or Missing | Not Present |
| | Tier 2c: "Detected" | Tier 4b: "Not Detected" | < drug tolerance limit of Tier 4b assay | Not Present |
| | Tier 2c: "Detected" | Tier 4b: "Not Detected" | ≥ drug tolerance limit of Tier 4b assay | Inconclusive |
| | Tier 2c: "Detected" | Tier 4b: "Detected" | < drug tolerance limit of Tier 4b assay | Present |
| | Tier 2c: "Detected" | Tier 4b: "Detected" | ≥ drug tolerance limit of Tier 4b assay | Present |

Abbreviations: ADA = antidiug antibody; Nab = neutralizing antibody; nGIP = native glucose-dependent insulinotropic polypeptide; nGLP-1 = native glucagon-like peptide-1; Tier 2b = cross-reactive ADA to nGIP; Tier 2c = cross-reactive ADA to nGLP-1; Tier 4a = Nab LY (tirzepatide) on GIPR; Tier 4b = Nab LY (tirzepatide) on GLP-1R.

Note: Only the drug tolerance limits of the Tier 4a and 4b assays are used for in silico classifications as they are lower than the drug tolerance limits of the Tier 2b and 2c assays, respectively.

4.6.3.5.2. Definitions of Immunogenicity Assessment Periods

Immunogenicity baseline observations: Baseline period for immunogenicity assessment for each participant includes all observations prior to first dose of study treatment. In instances where multiple baseline observations are collected, to determine participant ADA status the last nonmissing immunogenicity assessment prior to first administration of study drug is used to determine treatment-emergent status (see below).

Immunogenicity postbaseline period observations: Postbaseline period observations for each participant includes all observations after the first administration of study drug.

4.6.3.5.3. Definitions of Participant ADA Status

TE ADA-evaluable participants: A participant with a nonmissing baseline ADA result and at least 1 nonmissing postbaseline ADA result.

TE ADA-unevaluable participant: any participant who does not meet the evaluable criteria.

Baseline ADA Present (preexisting antibody): ADA detected in a sample collected up to the first dose date and time.

Baseline ADA Not Present: ADA is not detected, and the corresponding PK concentration is missing or below the drug tolerance limit in a sample collected up to the first dose date and time.

TE ADA+ participant: An evaluable participant who had a:

- baseline status of ADA Not Present and at least 1 postbaseline status of ADA Present with titer $\geq 2 \times$ MRD, where the MRD is the minimum required dilution of the ADA assay or
- baseline and postbaseline status of ADA Present, with the postbaseline titer being 2 dilutions (4-fold) greater than the baseline titer. That is, the participant has baseline (B) status of ADA Present, with titer 1:B, and at least 1 postbaseline (P) status of ADA Present, with titer 1:P, with P/B ≥ 4 .

As shown in [Figure GPIF.4.1](#), a titer is expected when ADA assay result is Detected. On occasion, the corresponding assay cannot be performed, in which case a titer value will be imputed for the purpose of TE ADA determination. A baseline sample with detected ADA and no titer is imputed to be the MRD (1:10), and a postbaseline sample with ADA detected and no titer is imputed to be 1 dilution above the MRD (1:20).

TE ADA- Inconclusive participant: A TE ADA-evaluable participant is TE ADA Inconclusive if $\geq 20\%$ of the participant's postbaseline samples, drawn predose, are ADA Inconclusive and all remaining postbaseline samples are ADA Not Present.

TE ADA- participant: A TE ADA-evaluable participant is TE ADA- when the participant is not TE ADA+ and not TE ADA Inconclusive.

For each Nab assay, the following are defined:

Nab+ participant: A participant who is TE ADA+ and has a Nab+ sample in the postbaseline period.

Nab Inconclusive participant: A participant who is TE ADA+, is not Nab+, and all samples that have TE ADA+ titer have a Nab Inconclusive sample result.

Nab- participant: A participant is neither Nab+ nor Nab Inconclusive.

Unless specified otherwise, the above-mentioned definitions of Nab are applicable to all Nab analyses, including cross-reactive Nab analyses, and cross-reactive antibodies.

4.6.3.5.4. Analyses to be Performed

The count and proportion of participants who are TE ADA+ will be tabulated by treatment group, where the proportions are relative to the number of TE ADA-evaluable participants, as defined above. The tabulation will include the count and proportion of participants with ADA Present at baseline, and the count and proportion of TE ADA+ participants exhibiting each type of cross-reactive antibodies and Nab. This analysis will be performed for the planned treatment

period. The cross-reactive Nab will include the *in silico* classification as cross-reactive Nab for summary.

Additional immunogenicity analyses as determined later may be presented. The relationship between the presence of antibodies and tirzepatide PK and pharmacodynamic response including safety and efficacy to tirzepatide may be assessed.

4.6.3.6. Hypersensitivity Reactions

Two main analyses are performed in support of assessment of potential immediate hypersensitivity, including anaphylaxis as well as potential nonimmediate hypersensitivity.

Time Period A, of potential immediate hypersensitivity includes all TEAEs occurring from start of study drug administration up to 24 hours after end of study drug administration. For events without the hypersensitivity eCRF, only date (no time) information is collected. Among these events without time information, the event occurred on the same date as the study drug injection date will be included in Time Period A.

Time Period B, of potential non-immediate hypersensitivity, includes all TEAEs occurring more than 24 hours after the end of study drug administration, but prior to subsequent drug administration.

Analyses for both time periods are based on the following:

- narrow and algorithm terms in *Anaphylactic reaction* SMQ (20000021) (analysis for algorithm term only applicable for Time Period A)
- narrow terms in *Angioedema* SMQ (20000024)
- narrow terms in *Severe cutaneous adverse reactions* SMQ (20000020), and
- narrow terms in *Hypersensitivity* SMQ (20000214)

For the *Anaphylactic reaction* SMQ, each term is classified by scope (narrow, broad) and by category (A, B, C, and D). All narrow terms are category A, and all broad terms are category B, C, or D. In addition to the usual narrow and broad searches, the SMQ defines an algorithm to further refine the cases of interest. For Time Period A analysis, the *Anaphylactic reaction* SMQ algorithm will be included. The algorithm is based upon events that occur within Time Period A. The counts and percentages of participants who experienced a TEAE for the following will be analyzed for each of the 2 time periods:

- any narrow term from any 1 of the 4 SMQs indicated above (that is, combined search across narrow of all 4 SMQs), and
- any narrow scope term within each SMQ, separately (that is, narrow SMQ search). For Time Period A analysis, any term from Anaphylactic reaction SMQ algorithm.

Within each query, individual PTs that satisfied the queries will be summarized. For Time Period A analysis, the Anaphylactic reaction SMQ algorithm will be summarized. Also, a single event may satisfy multiple SMQs, in which case the event contributes to every applicable SMQ.

4.6.3.6.1. Severe/Serious Hypersensitivity Reactions

The severe/serious cases of hypersensitivity will be considered as AESIs. Summary of severe/serious hypersensitivity reactions or listing may be provided.

4.6.3.7. Injection Site Reaction

Injection site reaction, incidence and rates, and related information reported via “Injection Site Reactions” eCRF will be summarized by treatment. Information to be summarized include location of the reaction, timing of reaction relative to study drug administration, and characteristics of the injection site reaction: erythema, induration, pain, pruritus, and edema.

Patient-based analysis and event-based analysis may be provided if necessary. The patient-based analysis summarizes all ISR questionnaire forms for an individual participant with a single statistic, typically an extreme value. This analysis allows each participant to contribute only once for each parameter, at the expense of a focus on the most extreme events. By contrast, the event-based analysis summarizes all ISR questionnaire forms received, without regard to individual participants. This provides characteristics of ISR events as a proportion of all events for which questionnaire responses were provided, at the expense of some potential bias due to differential contribution of individual participants to the analysis.

The counts and percentages of participants with treatment-emergent injection site reaction will be summarized by treatment using the MedDRA PTs. Detailed searching criteria can be found in Appendix 2 (Section 6.2).

The PTs will be summarized in decreasing order of incidence for tirzepatide-treated participants.

4.6.3.7.1. Severe/Serious Injection Site Reactions

Severe/serious injection site reactions (for example, abscess, cellulitis, erythema, hematomas/hemorrhage, exfoliation/necrosis, pain, subcutaneous nodules, swelling, induration, inflammation) will be considered as AESI.

The counts and percentage of participants with severe/serious ISRs may be summarized by treatment, or a listing of participants with treatment-emergent severe/serious ISRs may be provided.

4.6.3.8. Major Adverse Cardiovascular Events

MACE reported by investigators are adjudicated by an independent clinical endpoint committee in a blinded fashion. Unreported events may also be independently identified by the clinical endpoint committee.

The following positively adjudicated MACE will be considered as AESIs:

- death due to cardiovascular AEs
- myocardial infarction
- hospitalization for unstable angina
- hospitalization for heart failure
- coronary interventions (such as coronary artery bypass graft or percutaneous coronary intervention), and

- cerebrovascular events, including cerebrovascular accident (stroke) and transient ischemic attack.

The counts and percentages of participants with adjudicated MACE may be summarized by treatment. In addition, MACE reported by investigator may also be summarized although a MACE reported by investigator that is not positively adjudicated is not considered an AESI.

A listing of participants reporting MACE events, either reported by investigator or identified by the clinical endpoint committee, may be provided.

4.6.3.9. Major Depressive Disorder/Suicidal Ideation or Behavior

The severe/serious treatment-emergent major depressive disorder/suicidal ideation or behavior will be captured as AESI. AEs will be searched using MedDRA PT terms. Detailed searching criteria can be found in Appendix 2 (Section 6.2).

The counts and percentages of participants with TEAEs will be summarized by treatment group using MedDRA PT nested within SMQ. Events will be ordered by decreasing frequency in the total tirzepatide group nested within SMQ. A listing of participants with major depressive disorder/suicidal ideation or behavior may be provided if deemed necessary.

Additionally, suicidal ideation and behavior, and depression will be assessed by the investigator via spontaneously reported AEs and through the use of the C-SSRS and the PHQ-9.

4.6.3.9.1. Patient Health Questionnaire

Total scores for the PHQ-9 range from 0 to 27 with total scores categorized as

- none (not depressed): 0 through 4
- mild: 5 through 9
- moderate: 10 through 14
- moderately severe: 15 through 19, and
- severe: 20 through 27.

Shift tables will be provided showing the counts and percentages of participants within each baseline category (maximum value) versus each postbaseline category (maximum value) by treatment.

Additionally, the following 3 outcomes of interest will be compared between treatments (based on the maximum value during baseline and postbaseline):

- any increase in depression category (that is, worsening of depression): includes participants in the none, mild, moderate, or moderately severe category during baseline and with at least 1 postbaseline measurement
- increase from No or Mild Depression to Moderate, Moderately Severe, or Severe Depression: includes participants in the none or mild depression category during baseline and with at least 1 postbaseline measurement, and
- increase from Mild or Moderate Depression to Moderately Severe or Severe Depression: includes participants in the mild or moderate depression category during baseline and with at least 1 postbaseline measurement.

4.6.3.9.2. *Suicidal Ideation and Behavior Solicited Through C-SSRS*

Suicide-related thoughts and behaviors occurring during the entire study period, based on the C-SSRS, will be summarized by treatment group. In particular, for each of the following suicide-related events, the counts and percentages of participants with the event will be summarized by treatment group:

- died by suicide
- nonfatal suicide attempt
- interrupted attempt
- aborted attempt
- preparatory acts or behavior
- active suicidal ideation with specific plan and intent
- active suicidal ideation with some intent to act without specific plan
- active suicidal ideation with any methods (no plan) without intent to act
- nonspecific active suicidal thoughts
- wish to be dead, and
- nonsuicidal, self-injurious behavior.

In addition, the counts and percentages of participants who experienced at least 1 of the composite measures will be presented. The participants with at least 1 postbaseline C-SSRS assessment are included. The composite measure is determined at each assessment by the “yes” or “no” responses in C-SSRS categories by the study participant:

- Category 1 – Wish to be Dead
- Category 2 – Non-specific Active Suicidal Thoughts
- Category 3 – Active Suicidal Ideation with Any Methods (Not Plan) without Intent to Act
- Category 4 – Active Suicidal Ideation with Some Intent to Act, without Specific Plan
- Category 5 – Active Suicidal Ideation with Specific Plan and Intent
- Category 6 – Preparatory Acts or Behavior
- Category 7 – Aborted Attempt
- Category 8 – Interrupted Attempt
- Category 9 – Actual Attempt (non-fatal), and
- Category 10 – Completed Suicide.

Composite endpoints of suicidal ideation and suicidal behavior based on the above categories are defined below:

- **Suicidal ideation:** A “yes” answer at any time during study to any 1 of the 5 suicidal ideation questions (Categories 1 through 5) on the C-SSRS.
- **Suicidal behavior:** A “yes” answer at any time during study to any 1 of the 5 suicidal behavior questions (Categories 6 through 10) on the C-SSRS.
- **Suicidal ideation or behavior:** A “yes” answer at any time during study to any 1 of the 10 suicidal ideation and behavior questions (Categories 1 through 10) on the C-SSRS.

A listing contains data for each participant with suicidal ideation, suicidal behavior, or nonsuicidal self-injurious behavior during the study by treatment and visit. Data from all visits

are displayed, regardless of a “yes” or “no” answer, for participants with any “yes” answer for suicidal ideation, suicidal behavior, or self-injurious behavior without suicidal intent.

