#### *Other medical*

20. History of clinically relevant medical, behavioral, or psychiatric disorder, other than OSA, that is associated with insomnia or excessive sleepiness.
21. Impaired renal function, defined as eGFR  $<30 \text{ mL/min/1.73 m}^2$ .
22. Have a known clinically significant gastric emptying abnormality (for example, severe gastroparesis or gastric outlet obstruction) or chronically take drugs that directly affect GI motility.
23. History of chronic or acute pancreatitis.
24. Thyroid-stimulating hormone outside of the range of 0.4 to 6.0 mIU/L at the screening visit.

**Note:** Participants receiving treatment for hypothyroidism may be included, provided their thyroid hormone replacement dose has been stable for at least 3 months.

**Note:** TSH values above the normal range can, in some patients, suggest subclinical hypothyroidism. If, in the investigator's opinion, the participant has subclinical

hypothyroidism and may require initiation of thyroid hormone replacement during the course of the study, the participant should be excluded from the study.

25. Have obesity induced by other endocrinologic disorders (for example, Cushing Syndrome) or diagnosed monogenetic or syndromic forms of obesity (for example, Melanocortin 4 Receptor deficiency or Prader-Willi Syndrome).
26. Are, in the judgment of the investigator, actively suicidal and therefore deemed to be at significant risk for suicide.
27. Have answered “yes” to either Question 4 or Question 5 on the “Suicidal Ideation” portion of the C-SSRS **or**  
have answered “yes” to any of the suicide-related behaviors on the “suicidal behavior” portion of the C-SSRS,  
**and** the ideation or behavior occurred within the past month.
28. PHQ-9 score of 15 or more at Visit 1 or 2, prior to randomization.
29. Uncontrolled hypertension (SBP  $\geq$ 160 mmHg and/or DBP  $\geq$ 100 mmHg) at Visit 1.
30. Any of the following CV conditions less than 3 months prior to randomization: acute MI, cerebrovascular accident (stroke), unstable angina, or hospitalization due to congestive heart failure.
31. History of (less than 3 months prior to Visit 1) or planned CV procedure.
32. Heart failure, including New York Heart Association Functional Classification Class IV
33. Have acute or chronic hepatitis, signs and symptoms of any other liver disease other than nonalcoholic fatty liver disease, or any of the following, as determined by the central laboratory during screening:

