  - an active or untreated malignancy (other than basal or squamous cell skin cancer, in situ carcinomas of the cervix, or in situ prostate cancer) after randomization
- onset of pregnancy in a female participant (see Sections 7.2 and 8.3.2)
- Suicidal Ideation and Behavior
  - PHQ-9 score  $\geq 15$ 
    - Participants should be referred to a Mental Health Professional (MHP) to assist in deciding whether the participant should be discontinued from study intervention. If a participant's psychiatric disorder can be adequately treated with psycho- and/or pharmacotherapy, then the participant, at the discretion of the Investigator (in agreement with the MHP), may be continued in the trial on randomly assigned therapy.
    - in addition, study intervention may be discontinued if participants:
      - answered "yes" to Question 4 or Question 5 on the "Suicidal Ideation" portion of the C-SSRS, **or**
      - answered "yes" to any of the suicide-related behaviors on the Suicidal Behavior portion of the C-SSRS.

A psychiatrist or appropriately trained professional may assist in the decision to discontinue the participant. The participant should be referred to a MHP for further evaluation and care.

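### The PHQ-9 outcome for worsening to a score of 15 or more leaves out participants with no depression at baseline, so no planned between-arm comparison isolates all new scores at the protocol's own threshold

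*SAP*

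**What the plan says.** SAP Section 4.6.3.9.1 divides the PHQ-9 total into five categories. The lowest is "none (not depressed): 0 through 4"; mild is 5 to 9 and moderate is 10 to 14. The top two are "moderately severe: 15 through 19, and" "severe: 20 through 27". The section plans shift tables of every baseline category against every postbaseline category, by treatment. It then adds that "the following 3 outcomes of interest will be compared between treatments (based on the maximum value during baseline and postbaseline"). The three are:

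- **Outcome 1:** "any increase in depression category (that is, worsening of depression): includes participants in the none, mild, moderate, or moderately severe category during baseline".
- **Outcome 2:** a rise from none or mild to moderate or worse, among participants with none or mild at baseline.
- **Outcome 3:** "increase from Mild or Moderate Depression to Moderately Severe or Severe Depression: includes participants in the mild or moderate depression category during baseline".

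Each also requires at least one postbaseline measurement. SAP Section 4.6 makes Fisher's exact test the default for categorical safety responses.

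The protocol uses a score of 15 in two places. Exclusion criterion 28 in Section 5.2 is "PHQ-9 score of 15 or more at Visit 1 or 2, prior to randomization". Section 7.1 lists a score of 15 or more among the possible reasons for stopping study intervention and adds: "Participants should be referred to a Mental Health Professional (MHP) to assist in deciding whether the participant should be discontinued from study intervention".

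**The concern.** Outcome 3 is the only compared outcome whose event is exactly a PHQ-9 score of 15 or more. Because of criterion 28, essentially every randomized participant starts below 15, including those scoring 0 to 4. The natural safety question is whether more participants on one arm newly crossed the score at which the protocol asks for a referral. As defined, outcome 3 answers it only for those who already had mild or moderate symptoms. It leaves out the largest deterioration the scale allows, from none to severe.

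Protocol Section 8.2.6 names the PHQ-9 as a monitoring tool for suicidal ideation and behavior, and Section 8.3.3 lists major depressive disorder and suicidality as an adverse event of special interest. At stake is how directly the report shows any imbalance at the threshold. No efficacy conclusion is involved.

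**Working it through.** The plan gives no figure to reproduce here, so the check is an enumeration followed by an illustration under stated assumptions.

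**Step 1: enumerate.** Five ordered categories give 5 × 4 / 2 = 10 worsening transitions. A new score of 15 or more means a baseline of none, mild or moderate and a postbaseline value of moderately severe or severe.

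| Baseline → postbaseline | Outcome 1 | Outcome 2 | Outcome 3 | New ≥15 |
|---|---|---|---|---|
| none → mild | yes | no | no | no |
| none → moderate | yes | yes | no | no |
| none → moderately severe | yes | yes | **no** | **yes** |
| none → severe | yes | yes | **no** | **yes** |
| mild → moderate | yes | yes | no | no |
| mild → moderately severe | yes | yes | yes | yes |
| mild → severe | yes | yes | yes | yes |
| moderate → moderately severe | yes | no | yes | yes |
| moderate → severe | yes | no | yes | yes |
| moderately severe → severe | yes | no | no | no |

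Six transitions give a new score of 15 or more.

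- Outcome 1 contains all 6, mixed with 4 that do not.
- Outcome 2 contains 4 of the 6, mixed with 2 that reach only 10 to 14, and misses the 2 from moderate.
- Outcome 3 contains 4 of the 6 and nothing else, and misses the 2 from none.

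No compared outcome equals the target set. Adding none to the baseline set of outcome 3 gives 6 of 6 with nothing extra.

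**Step 2: denominator.** The documents plan about 103 participants per arm but give no baseline PHQ-9 distribution. Let p be the share scoring 0 to 4 at baseline (assumed). Outcome 3 keeps 103 × (1 − p):

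- p = 0.30: 103 × 0.70 ≈ 72 per arm
- p = 0.75: 103 × 0.25 ≈ 26 per arm

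**Step 3: share of new cases outside outcome 3.** Let r₀ be the risk of reaching 15 or more from none and r₁ the risk from mild or moderate. The documents give neither. Then

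share = p·r₀ / [p·r₀ + (1 − p)·r₁].

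With r₁ = 6% throughout:

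| p | r₀ | Calculation | Share outside outcome 3 |
|---|---|---|---|
| 0.30 | 0.5% | 0.0015 / (0.0015 + 0.0420) | about 3% |
| 0.65 | 1% | 0.0065 / (0.0065 + 0.0210) | about 24% |
| 0.65 | 3% | 0.0195 / (0.0195 + 0.0210) | about 48% |
| 0.75 | 3% | 0.0225 / (0.0225 + 0.0150) | 60% |

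**Step 4: expected counts.** At p = 0.65, r₀ = 3% and r₁ = 6%, an arm of 103 has 103 × 0.0195 ≈ 2 cases from none and 103 × 0.0210 ≈ 2 from mild or moderate. Even with the widened outcome, 4 of 103 against 8 of 103 gives a two-sided Fisher p of 0.37.

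**The case against.** The strongest reply is that nothing is lost. Every new score of 15 or more is an event in outcome 1, and outcomes 2 and 3 together also cover all six transitions. The by-treatment shift tables show the two missing transitions as separate cells, so a reader can total the new cases per arm. This stands. A reader who looks only at outcome 3 might infer that a worsening from none to severe goes uncounted, or that no arm comparison captures new scores of 15 or more. The documents support neither reading. What is missing is isolation: one compared outcome that contains these cases and no others. Section 4.6.3.9.1 names no comparison of the summed shift-table cells, and a test of the whole shift distribution would not single them out.

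The second reply is that the special-interest event does not depend on this outcome. In SAP Section 4.6.3.9 and Appendix 2 it is defined by severe or serious treatment-emergent events found through MedDRA queries, and the C-SSRS is summarized separately. The referral in Protocol Section 7.1 applies to the individual whatever is tabulated. This also stands, and it limits the importance of the point. Adverse event tables are not a complete substitute, though. Protocol Section 8.3.1.1 tells sites not to amend the adverse event form for a suicide-related event found only through the PHQ-9 or C-SSRS, unless it is serious or leads to discontinuation.

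The third reply is that events will be few and a formal test weak. On the rates in Step 4 that is right. The benefit is a clear count on the right denominator more than a gain in power.

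**Conclusion.** The gap is real and small. Outcome 3 has the right event and too narrow a baseline set: it counts 4 of the 6 transitions to a new score of 15 or more. No prespecified between-arm comparison therefore isolates all such cases, although 15 is the score the protocol uses for both exclusion and referral. Cases from none are counted within outcomes 1 and 2 and shown in the shift tables.

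That conclusion rests only on the SAP definitions. Its numerical size is not known. The 3% to 60% range depends on assumed values (30% to 75% with none at baseline, 0.5% to 3% of them and 6% of the mild or moderate group reaching 15) and describes cases outside outcome 3, not cases missing from the report. The documents do not show that a real imbalance would go unseen. Efficacy analyses and type 1 error control are unaffected. This is a worthwhile improvement to safety reporting and not a condition for the trial's conclusions.

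**What to change.** In SAP Section 4.6.3.9.1, redefine outcome 3 as an increase from none, mild or moderate to moderately severe or severe (PHQ-9 of 15 or more). Include every participant with a baseline PHQ-9 below 15 and at least one postbaseline measurement, and compare arms by Fisher's exact test, the Section 4.6 default. Keep the current mild-or-moderate version as a subset row. Outcomes 1 and 2 and the shift tables can stay as they are.

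The cost is one sentence in the SAP and one table row, from data already collected. No clinical rule changes.
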